12.1.8 Subgroup/Subset Analyses

Subgroup/subset analyses will be conducted based on baseline EYO (EYO \leq 0 vs EYO $>$ 0), baseline CDR (CDR=0 vs CDR $>$ 0), and target biomarker at baseline (above vs. at or below the median). Additional subset analyses are defined in the drug-specific appendices. The goal of these analyses is to demonstrate the treatment effect for each subgroup/subset.

The following analyses will be conducted for the combined population of the mITT population and the eligible DIAN-OBS subjects.

- (i) An indicator variable will be generated for the mutation positive subjects in the active drug arms to indicate which subjects have EYO \leq 0 at baseline and which have EYO $>$ 0 at baseline. Each active drug arm will be divided into two subsets using this indicator. The MDPM will estimate 5 CPRs. One is the ratio of the mutation positive placebo arm to the eligible DIAN-OBS arm (denoted as e^{θ_2}); one is the gantenerumab active drug EYO \leq 0 arm to the eligible DIAN-OBS subjects arm (denoted as e^{θ_3}); one is the gantenerumab active drug EYO $>$ 0 arm to the eligible DIAN-OBS arm (denoted as e^{θ_4}); one is the solanezumab active drug EYO \leq 0 arm to the eligible DIAN-OBS arm (denoted as e^{θ_5}), and one is the solanezumab active drug EYO $>$ 0 arm to the eligible DIAN-OBS arm (denoted as e^{θ_6}). The treatment effect for the gantenerumab active drug EYO \leq 0 arm, will be estimated indirectly using the posterior samples as $e^{\theta_3 - \theta_2}$ (or equivalently $\frac{e^{\theta_3}}{e^{\theta_2}}$); for the gantenerumab active drug EYO $>$ 0 arm, it will be estimated indirectly using the posterior samples as $e^{\theta_4 - \theta_2}$ (or equivalently $\frac{e^{\theta_4}}{e^{\theta_2}}$); for the solanezumab active drug EYO \leq 0 arm, it will be estimated indirectly using the posterior samples as $e^{\theta_5 - \theta_2}$ (or equivalently $\frac{e^{\theta_5}}{e^{\theta_2}}$); for the solanezumab active drug EYO $>$ 0 arm, it will be estimated indirectly using the posterior samples as

$e^{\theta_6 - \theta_2}$ (or equivalently $\frac{e^{\theta_6}}{e^{\theta_2}}$). The difference in the treatment effect for EYO ≤ 0 and EYO > 0 will be estimated indirectly using the posterior samples as $e^{\theta_3 - \theta_4}$ (or equivalently $\frac{e^{\theta_3}}{e^{\theta_4}}$) for gantenerumab, and indirectly using the posterior samples as $e^{\theta_5 - \theta_6}$ (or equivalently $\frac{e^{\theta_5}}{e^{\theta_6}}$) for solanezumab. All the other parameters in the MDPM will be set up similarly to those in SAP [Section 12.1.3](#). This analysis will be done in a single run of the MDPM.

- (ii) If the study drug has a targeted biomarker then an indicator will be generated for subjects above and subjects at or below the median target biomarker at baseline for the active drug arm. The MDPM will estimate 5 CPRs. One is the ratio of the mutation positive placebo arm to the eligible DIAN-OBS subjects arm (denoted as e^{θ_2}); one is the gantenerumab active drug, biomarker above median value arm to the eligible DIAN-OBS arm (denoted as e^{θ_3}); one is the gantenerumab active drug, biomarker at or below the median arm value to the eligible DIAN-OBS arm (denoted as e^{θ_4}); one is the solanezumab active drug, biomarker above median value arm to the eligible DIAN-OBS arm (denoted as e^{θ_5}), and one is the solanezumab active drug, biomarker at or below the median arm to the eligible DIAN-OBS arm (denoted as e^{θ_6}). The treatment effect for the gantenerumab active drug, biomarker above the median value arm will be estimated indirectly using the posterior samples as $e^{\theta_3 - \theta_2}$ (or equivalently $\frac{e^{\theta_3}}{e^{\theta_2}}$); for the gantenerumab active drug, biomarker at or below the median arm will be estimated indirectly using the posterior samples as $e^{\theta_4 - \theta_2}$ (or equivalently $\frac{e^{\theta_4}}{e^{\theta_2}}$); for the solanezumab active drug, biomarker above the median value arm will be estimated indirectly using the posterior samples as $e^{\theta_5 - \theta_2}$ (or equivalently $\frac{e^{\theta_5}}{e^{\theta_2}}$); and for the solanezumab active drug, biomarker at or below the median arm will be estimated indirectly using the posterior samples as $e^{\theta_6 - \theta_2}$ (or equivalently $\frac{e^{\theta_6}}{e^{\theta_2}}$). The difference in the treatment effect for biomarker above the median value and biomarker at or below the median value will be estimated indirectly using the posterior samples as $e^{\theta_3 - \theta_4}$ (or equivalently $\frac{e^{\theta_3}}{e^{\theta_4}}$) for gantenerumab, and indirectly using the posterior samples as $e^{\theta_5 - \theta_6}$ (or equivalently $\frac{e^{\theta_5}}{e^{\theta_6}}$) for solanezumab. All the other parameters in the

MDPM will be set up similarly to those in SAP [Section 12.1.3](#). This analysis will be done in a single run of the MDPM.

- (iii) An indicator variable will be generated for mutation positive subjects in the active drug arms to indicate which subjects have CDR = 0 at baseline and which ones have CDR > 0 at baseline. Each active drug arm will be divided into two subsets using this indicator. The MDPM will estimate 5 CPRs. One is the ratio of the mutation positive placebo arm to the eligible DIAN-OBS subjects arm (denoted as e^{θ_2}); one is the gantenerumab active drug CDR = 0 arm to the eligible DIAN-OBS arm (denoted as e^{θ_3}); one is the gantenerumab active drug CDR > 0 arm to the eligible DIAN-OBS arm (denoted as e^{θ_4}); one is the solanezumab active drug CDR = 0 arm to the eligible DIAN-OBS subjects arm (denoted as e^{θ_5}); and one is the solanezumab active drug CDR > 0 arm to the eligible DIAN-OBS arm (denoted as e^{θ_6}). The treatment effect for the gantenerumab active drug CDR = 0 arm will be estimated indirectly using the posterior samples as $e^{\theta_3 - \theta_2}$ (or equivalently $\frac{e^{\theta_3}}{e^{\theta_2}}$); for the gantenerumab active drug CDR > 0 arm, the treatment effect will be estimated indirectly using the posterior samples as $e^{\theta_4 - \theta_2}$ (or equivalently $\frac{e^{\theta_4}}{e^{\theta_2}}$); for the solanezumab active drug CDR = 0, it will be estimated indirectly using the posterior samples as $e^{\theta_5 - \theta_2}$ (or equivalently $\frac{e^{\theta_5}}{e^{\theta_2}}$); and for the solanezumab active drug CDR > 0 arm, it will be estimated indirectly using the posterior samples as $e^{\theta_6 - \theta_2}$ (or equivalently $\frac{e^{\theta_6}}{e^{\theta_2}}$). The difference in the treatment effect for CDR = 0 and CDR > 0 will be estimated indirectly using the posterior samples as $e^{\theta_3 - \theta_4}$ (or equivalently $\frac{e^{\theta_3}}{e^{\theta_4}}$) for gantenerumab, and indirectly using the posterior samples as $e^{\theta_5 - \theta_6}$ (or equivalently $\frac{e^{\theta_5}}{e^{\theta_6}}$) for solanezumab. All their other parameters in the MDPM will be set up similarly to those in SAP [Section 12.1.3](#). This analysis will be done in a single run of the MDPM.

These subgroup/subset analyses will also be conducted using the following LME model. These analyses will be conducted for each component of DIAN-MCE, for the DIAN-TU cognitive composite, and for the secondary endpoints. For ISLT and the DIAN-TU cognitive composite, these analyses will be done on the mITT population; whereas for the others, these analyses will be done on the mITT population, and on the mITT population and the eligible DIAN-OBS subjects.

The first model below will estimate the average treatment effect for each sub-group:

$$y_{ij} = (\beta_0 + u_{0i}) + \beta_1 * Disease_{status_i} + (\beta_2 + u_{1i}) * t_{ij} + \beta_3 * Disease_{status_i} * t_{ij} + \beta_4 * Gant_i * \max(0, t_{ij}) + \beta_5 * Gant_i * \max(0, t_{ij}) * Disease_{status_i} + \beta_6 * Sola_i * \max(0, t_{ij}) + \beta_7 * Sola_i * \max(0, t_{ij}) * Disease_{status_i} + \varepsilon_{ij},$$

where y_{ij} denotes the longitudinal assessments for subject i at time t_{ij} ; $Sola_i = 1$ for the active solanezumab arm, $Sola_i = 0$, otherwise; $Gant_i = 1$ for the active gantenerumab arm, $Gant_i = 0$, otherwise; u_{0i}, u_{1i} are the random effects for the intercept and the slope and follow a bivariate normal distribution $\begin{pmatrix} u_{0i} \\ u_{1i} \end{pmatrix} \sim N\left(0, \begin{bmatrix} \sigma_{u_{0i}}^2 & \sigma_{u_{0i}u_{1i}} \\ \sigma_{u_{0i}u_{1i}} & \sigma_{u_{1i}}^2 \end{bmatrix}\right)$; and the residual follows a normal distribution $\varepsilon_{ij} \sim N(0, \sigma_e^2)$. The disease status will be defined for each outcome. For baseline EYO, $Disease_{status_i} = 1$ for baseline EYO > 0, $Disease_{status_i} = 0$ otherwise; for targeted biomarker, $Disease_{status_i} = 1$ for baseline biomarker > median, $Disease_{status_i} = 0$ otherwise; for baseline CDR, $Disease_{status_i} = 1$ if baseline CDR > 0; $Disease_{status_i} = 0$ otherwise; and this variable will be treated as categorical.

For DIAN-TU-001 subjects:

- (i) t_{ij} is the time since baseline randomization, $t_{ij} = 0$ at the baseline, $t_{ij} < 0$ for the run-in visits, $t_{ij} > 0$ for post-randomization visit; $t_{ij} < 0$ is not applicable when the model only includes DIAN-TU-001 subjects without run-in data;
- (ii) $\max(0, t_{ij}) = 0$ if $t_{ij} \leq 0$; $\max(0, t_{ij}) = t_{ij}$ if $t_{ij} > 0$;
- (iii) CDR/EYO/target biomarker at randomization ($t_{ij} = 0$) is used to define disease status.

For eligible DIAN-OBS, non-run-in subjects:

- (i) $t_{ij} = 0$ for baseline DIAN-OBS visit, $t_{ij} > 0$ for post-baseline visit;
- (ii) CDR/EYO/target biomarker at DIAN-OBS baseline ($t_{ij} = 0$) is used to define disease status.

In this model, β_4 is the treatment effect of gantenerumab for subjects with baseline disease status 0; β_5 is the treatment effect difference of gantenerumab for subjects with baseline disease status 1 relative to those with baseline disease status 0; β_6 is the treatment effect of solanezumab for

subjects with baseline disease status 0; β_7 is the treatment effect difference of solanezumab for subjects with baseline disease status 1 relative to those with baseline disease status 0.

The second model below will estimate the treatment effect of low/high doses separately for each sub-group:

$$y_{ij} = (\beta_0 + u_{0i}) + \beta_1 * Disease_{status_i} + (\beta_2 + u_{1i}) * t_{ij} + \beta_3 * Disease_{status_i} * t_{ij} + \beta_4 * Gant_i * \max(0, t_{ij}) + \beta_5 * Gant_i * \max(0, t_{ij}) * Disease_{status_i} + \beta_6 * \max(0, t_{ij} - titration_{time_i}) * Gant_i + \beta_7 * \max(0, t_{ij} - titration_{time_i}) * Gant_i * Disease_{status_i} + \beta_8 * Sola_i * \max(0, t_{ij}) + \beta_9 * Sola_i * \max(0, t_{ij}) * Disease_{status_i} + \beta_{10} * \max(0, t_{ij} - titration_{time_i}) * Sola_i + \beta_{11} * \max(0, t_{ij} - titration_{time_i}) * Sola_i * Disease_{status_i} + \varepsilon_{ij},$$

where y_{ij} denotes the longitudinal assessments for subject i at time t_{ij} ; $Sola_i = 1$ for the active solanezumab arm, $Sola_i = 0$, otherwise; $Gant_i = 1$ for the active gantenerumab arm, $Gant_i = 0$, otherwise; u_{0i}, u_{1i} are the random effects for the intercept and the slope and follow a bivariate normal distribution $\begin{pmatrix} u_{0i} \\ u_{1i} \end{pmatrix} \sim N\left(0, \begin{bmatrix} \sigma_{u_{0i}}^2 & \sigma_{u_{0i}u_{1i}} \\ \sigma_{u_{0i}u_{1i}} & \sigma_{u_{1i}}^2 \end{bmatrix}\right)$; the residual follows a normal distribution $\varepsilon_{ij} \sim N(0, \sigma_e^2)$; and the disease status will be defined for each outcome. For baseline EYO, $Disease_{status_i} = 1$ for baseline EYO > 0, $Disease_{status_i} = 0$ otherwise; for targeted biomarker, $Disease_{status_i} = 1$ for baseline biomarker > median, $Disease_{status_i} = 0$ otherwise; for baseline CDR, $Disease_{status_i} = 1$ if baseline CDR > 0; $Disease_{status_i} = 0$ otherwise; and this variable will be treated as categorical.

For DIAN-TU-001 subjects:

- (i) t_{ij} is the time since baseline randomization, $t_{ij} = 0$ at the baseline, $t_{ij} < 0$ for the run-in visits, $t_{ij} > 0$ for post-randomization visit;
- (ii) If $titration_{time_i}$ is missing then $\max(0, t_{ij} - titration_{time_i}) = 0$;
- (iii) For subjects on placebo, $\max(0, t_{ij} - titration_{time_i}) = 0$;
- (iv) $\max(0, t_{ij}) = 0$ if $t_{ij} \leq 0$; $\max(0, t_{ij}) = t_{ij}$ if $t_{ij} > 0$;
- (v) CDR/EYO/target biomarker at randomization ($t_{ij} = 0$) is used to define disease status.

For eligible DIAN-OBS, non-run-in subjects:

- (i) $t_{ij} = 0$ for baseline DIAN-OBS visit, $t_{ij} > 0$ for post-baseline visit;
- (ii) CDR/EYO/target biomarker at DIAN-OBS baseline ($t_{ij} = 0$) is used to define disease status;
- (iii) $\max(0, t_{ij} - \text{titration}_{\text{time}_i}) = 0$.

In this model, β_4 is the treatment effect of gantenerumab low dose for subjects with baseline disease status 0; β_5 is the treatment effect difference of gantenerumab low dose for subjects with baseline disease status 1 relative to those with baseline disease status 0; β_6 is the treatment effect of gantenerumab high doses for subjects with baseline disease status 0; β_7 is the treatment effect difference of gantenerumab high doses for subjects with baseline disease status 1 relative to those with baseline disease status 0. The coefficient β_8 is the treatment effect of solanezumab low dose for subjects with baseline disease status 0; β_9 is the treatment effect of solanezumab low dose for subjects with baseline disease status 1 relative to those with baseline disease status 0; β_{10} is the treatment effect of solanezumab high doses for subjects with baseline disease status 0; β_{11} is the treatment effect difference of solanezumab high doses for subjects with baseline disease status 1 relative to those with baseline disease status 0.

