where y_{ij} denotes the longitudinal assessments for subject i at time t_{ij} ; $Sola_i = 1$ for the active solanezumab arm, $Sola_i = 0$, otherwise; $Gant_i = 1$ for the active gantenerumab arm, $Gant_i = 0$; u_{0i}, u_{1i} are the random effects for the intercept and the slope and follow a bivariate normal distribution $\begin{pmatrix} u_{0i} \\ u_{1i} \end{pmatrix} \sim N\left(0, \begin{bmatrix} \sigma_{u_{0i}}^2 & \sigma_{u_{0i}u_{1i}} \\ \sigma_{u_{0i}u_{1i}} & \sigma_{u_{1i}}^2 \end{bmatrix}\right)$; the residual follows normal distributions $\varepsilon_{ij} \sim N(0, \sigma_e^2)$; $Disease_{status_i} = 1$ if baseline CDR >0 ; $Disease_{status_i} = 0$ otherwise; and this variable will be treated as categorical.

For DIAN-TU-001 subjects:

- (i) t_{ij} is the time since the baseline randomization, $t_{ij} = 0$ at the baseline, $t_{ij} < 0$ for the run-in visits, $t_{ij} > 0$ for the post-randomization visit;
- (ii) If $titration_{time_i}$ is missing, then $\max(0, t_{ij} - titration_{time_i}) = 0$;
- (iii) For subjects on placebo, $\max(0, t_{ij} - titration_{time_i}) = 0$;
- (iv) $\max(0, t_{ij}) = 0$ if $t_{ij} \leq 0$; $\max(0, t_{ij}) = t_{ij}$ if $t_{ij} > 0$;
- (v) CDR at randomization ($t_{ij} = 0$) is used to define the disease status.

For eligible DIAN-OBS, non-run-in subjects:

- (i) $t_{ij} = 0$ for the baseline DIAN-OBS visit, $t_{ij} > 0$ for the post-baseline visit;
- (ii) CDR at the DIAN-OBS baseline ($t_{ij} = 0$) is used to define the disease status;
- (iii) $\max(0, t_{ij} - titration_{time_i}) = 0$.

Hypothesis testing for the gantenerumab **high dose** treatment effect:

$$H_0: \beta_4 + \beta_6 = 0, H_0: \beta_4 + \beta_6 \neq 0.$$

Hypothesis testing for the solanezumab **high dose** treatment effect:

$$H_0: \beta_5 + \beta_7 = 0, H_0: \beta_5 + \beta_7 \neq 0.$$

The model will be run on the following 3 groups, respectively:

- i) the active solanezumab drug, the active gantenerumab drug, and the mutation positive placebo arm,
- ii) the active solanezumab drug, the active gantenerumab drug, and the combination of the mutation positive placebo arm and the eligible DIAN-OBS subjects as a single arm.

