12.4.3.4 Subgroup/subset analyses for CDR-SB and FAS

CDR-SB and FAS will be analyzed using the models/population (mITT only, mITT and eligible DIAN-OBS subjects) specified in [Section 12.1.8](#).

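### The second LME model in SAP 12.1.8 labels changes of slope at titration as high-dose effects; the high-dose effect is a sum of coefficients, as 12.1.7 has it

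*SAP*

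**What the plan says.** Section 12.1.8 introduces the model as follows: "The second model below will estimate the treatment effect of low/high doses separately for each sub-group". For gantenerumab the equation contains:

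- β4, multiplying max(0, t), and β5, multiplying max(0, t) × disease status;
- a titration term, "\beta_6 * \max(0, t_{ij} - titration_{time_i}) * Gant_i", and β7 on its product with disease status.

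Solanezumab has the same four terms with β8 to β11. The notes under the model define max(0, t) as t for every positive t, with no stop at titration. They set the titration terms to zero for placebo and DIAN-OBS non-run-in subjects.

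The closing paragraph of 12.1.8 then interprets the coefficients. It says that β6 "is the treatment effect of gantenerumab high doses for subjects with baseline disease status 0". For β7 it gives this reading: "is the treatment effect difference of gantenerumab high doses for subjects with baseline disease status 1 relative to those with baseline disease status 0". β10 and β11 are described the same way for solanezumab. No hypothesis or contrast is given for this model.

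Section 12.1.7 has the same piecewise form without the subgroup interactions. It states the gantenerumab high-dose null hypothesis as "H_0: \beta_4 + \beta_6 = 0", and uses the matching sum β5+β7 for solanezumab. The sensitivity model in Section 4.2 of the gantenerumab appendix (SAP Appendix VII) tests the same sums.

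**The concern.** A term in max(0, t − titration time), added to a term in max(0, t), measures how much the slope changes at titration. It does not measure the slope difference from control after titration. The two agree only if the low-dose coefficient is exactly zero. As labelled, the output would answer whether the slope changed when the dose went up and present this as whether the high dose works.

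The model is planned for each component of DIAN-MCE, the cognitive composite and the secondary endpoints. Section 12.4.3.4 reuses it: "CDR-SB and FAS will be analyzed using the models/population" of 12.1.8. Section 4.1 of the gantenerumab appendix applies 12.1.8 to the baseline PiB subset. It is also the only specified source of subgroup-by-dose estimates, because the disease progression model (MDPM) subgroup analyses have one progression ratio per subgroup and drug, with no split by dose.

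**Working it through.** **Inputs.** The equation and notes are those of the second LME model in Section 12.1.8. Write D for disease status (0 or 1) and T for titration time. Take a gantenerumab subject (Gant = 1, Sola = 0).

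**Slopes in t for t > 0**

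- Control: β2 + β3·D
- Active, before titration: β2 + β3·D + β4 + β5·D
- Active, after titration: β2 + β3·D + β4 + β5·D + β6 + β7·D

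**Active minus control**

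- Low dose: β4 + β5·D
- High dose: (β4+β6) + (β5+β7)·D

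| Quantity | Section 12.1.8 says | The equation gives |
|---|---|---|
| Gantenerumab, high dose, status 0 | β6 | β4+β6 |
| Gantenerumab, high dose, status 1 minus status 0 | β7 | β5+β7 |
| Solanezumab, high dose, status 0 | β10 | β8+β10 |
| Solanezumab, high dose, status 1 minus status 0 | β11 | β9+β11 |

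The error in each label is the matching low-dose coefficient. It is β4 or β8 for the status 0 effect, and β5 or β9 (the low-dose subgroup difference) for the subgroup contrast.

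**Numerical check.** The SAP gives no slope effects by dose, so those below are assumptions, in points per year with positive meaning slower decline. Noise-free data were built with known low-dose and high-dose slope effects, half-yearly visits to year 5 and titration at 1, 2 or 3 years (the times used in scenario F of SAP Appendix VI). The stated fixed-effect terms were then fitted by least squares.

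| True effect, status 0 (low / high) | True subgroup difference (low / high) | β4 | β6 | β4+β6 | β5 | β7 | β5+β7 |
|---|---|---|---|---|---|---|---|
| 0.10 / 0.10 | 0.05 / 0.05 | 0.10 | 0.00 | 0.10 | 0.05 | 0.00 | 0.05 |
| 0.10 / 0.15 | 0.02 / 0.05 | 0.10 | 0.05 | 0.15 | 0.02 | 0.03 | 0.05 |
| 0.10 / 0.05 | 0.05 / 0.02 | 0.10 | −0.05 | 0.05 | 0.05 | −0.03 | 0.02 |
| 0 / 0.15 | 0 / 0.05 | 0 | 0.15 | 0.15 | 0 | 0.05 | 0.05 |

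The sums recover the true high-dose values in every row. β6 and β7 alone do so only in the last row, where the low dose has no effect. In the first row a real high-dose effect is reported as zero. In the third a real benefit is reported as harm. The error can also inflate: a low-dose effect of −0.05 and a high-dose effect of +0.05 give β6 = 0.05 − (−0.05) = 0.10, twice the true value.

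**Against the SAP's own dose assumptions.** The default simulations in Appendix VI take the low-dose effect as equal to the high-dose effect. Scenario F sets it to 0.75, 0.50, 0.25 or 0 of the high-dose effect. If those ratios r are carried to the slope scale as an illustration, β6 equals (1 − r) times the true high-dose effect. That is 0% of it under the default, and 25%, 50%, 75% and 100% under scenario F.

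**The case against.** The strongest reply is that the model is sound and only its description is wrong. The fit contains every parameter needed, so the correct contrasts can be taken from it at any time. Section 12.1.8 states no test for these coefficients, and the high-dose hypotheses printed elsewhere in the SAP are all sums. An analyst extending 12.1.7 to subgroups might well use the sum.

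The reach is also limited. The following are unaffected:

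- the primary four-arm MDPM;
- the MDPM subgroup analyses and the MDPM low/high-dose analysis;
- the first LME model of 12.1.8;
- the overall tests of 12.1.7;
- the fixed-sequence tests of CDR-SB and FAS for gantenerumab, which rest on the 12.1.7 model.

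The CDR-SB and FAS subgroup analyses sit under exploratory analyses.

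All of this stands as a limit on scope. It does not remove the error. Section 8.1 requires analyses to follow the SAP and deviations to be documented in the study report. The only instruction for reading this model is the incorrect one, and nothing in 12.1.8 carries the 12.1.7 sums across.

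**Conclusion.** The point holds. Section 12.1.8 misstates the meaning of β6, β7, β10 and β11 and contradicts Section 12.1.7 on what a high-dose effect is. If the stated definitions are followed, every subgroup high-dose effect from this model is wrong by the matching low-dose coefficient, and every high-dose subgroup difference by the low-dose subgroup difference. The conclusion is algebra on the printed equation and needs no distributional assumption; only the example slopes are assumed. The damage is confined to the second LME model of 12.1.8 and the analyses that reuse it. Within those, it can erase or reverse a reported effect, so it should be corrected before unblinding.

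**What to change.** Replace the coefficient readings at the end of Section 12.1.8 with these contrasts:

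| | Gantenerumab | Solanezumab |
|---|---|---|
| High dose, status 0 | β4+β6 | β8+β10 |
| High dose, status 1 | β4+β5+β6+β7 | β8+β9+β10+β11 |
| High dose, status 1 minus status 0 | β5+β7 | β9+β11 |

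Describe β6 and β10 as the change of slope at titration in status 0, and β7 and β11 as the subgroup difference in that change. Take standard errors from the full covariance matrix; for example, Var(β4+β6) = Var(β4) + Var(β6) + 2·Cov(β4, β6). In the same edit, call β9 a treatment effect difference, as is done for β5.

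An equivalent route is to replace max(0, t) in the low-dose terms with min(max(0, t), titration time), or with max(0, t) where titration time is missing. The coefficients would then carry the meanings now printed. The contrasts are preferable because they leave the model in the same form as 12.1.7.

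The cost is one paragraph of SAP wording and one estimate statement per contrast. The data, the fitted model and the other analyses do not change.
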